11.14 Laboratory assessments

All laboratory assessments will be performed centrally at one or more certified laboratories selected by ALK.

The clinical laboratory values will be reported to the investigator by the laboratory and he/she must immediately review them for clinical significance.

Laboratory assessments are described in a separate laboratory manual that also details blood sampling and shipment procedures.

The following laboratory variables will be measured:

Haematology - Automated differential

Haemoglobin, erythrocytes, haematocrit, mean corpuscular haemoglobin (MCH), mean corpuscular volume (MCV), platelets, leucocytes, neutrophils, lymphocytes, monocytes, eosinophils and basophils

Blood chemistry

Alanine aminotransferase (ALT)/serum glutamic pyruvic transaminase (SGPT), albumin, alkaline phosphatase, aspartate aminotransferase (AST)/serum glutamic-oxaloacetic transaminase (SGOT), blood urea nitrogen (BUN), calcium, chloride, creatinine, glucose, lactate dehydrogenase (LDH), potassium, sodium and total bilirubin

Clinical trial protocol	Date:	12-Nov-2021	
Trial ID: SU-G-01	Version:	4.0	ſ
EudraCT No. 2020-000455-12	Status:	Final	
CONFIDENTIAL	Page:	46 of 77	

Urinalysis

bilirubin, glucose, haemoglobin, ketone, leukocytes, nitrite, pH, protein, specific gravity and urobilinogen

lgE

To assess the inclusion criteria in order to confirm the diagnosis of allergy against grass, blood samples will be drawn at the screening visit (visit 1) for determination of specific IgE against the following allergens: *Phleum pratense*

These samples will be analysed together with the samples for the safety laboratory assessments (see above), and the results will be reported to sites for assessment of subject eligibility.

11.15 Long-term storage of samples

Blood sample for storage in Biobank

This blood sample will only be drawn if the subject consents to long-term storage of a blood sample.

If long-term sampling is accepted, a 5.0 ml blood sample will be drawn at visits 1 and 9 where blood sampling is already planned. The subject will consequently only donate an extra blood sample and no additional venipuncture is required.

The purpose of the biobank blood samples is to continue the research into the immunological processes involved in the observed clinical effects in subjects treated with allergy immunotherapy, and which today is not fully understood. One of the goals of this research is to identify one or more surrogate markers, which can predict clinical efficacy in the individual subject, i.e., which can help ensuring optimal treatment for future subjects with allergies. The surrogate markers may be antibody levels, cytokine profiles, cell surface markers, specific set of proteins or metabolites or combinations hereof, etc. Although the exploratory biomarker analyses will help to increase our understanding, the efforts described in this protocol are strictly research based. Thus, as the complex interactions between allergy immunotherapy, rhinoconjunctivitis and asthma are currently not characterised to a level that translates to a meaningful clinical advantage, individual results from the exploratory biomarker analyses will not be given to the subjects. For the same reasons, individual results will not be added to the subjects' medical records.

The subjects will have no direct benefit from the exploratory biomarker analyses.

The samples will be stored at ALK after end of trial and until marketing authorisation approval or until the research project terminates, but no longer than 25 years from end of trial after which they will be destroyed.

If ALK publishes results obtained from biomarker studies based on samples obtained in the trial, the results will be published in such a way that it cannot be tied to an individual subject.

Clinical trial protocol	Date:	12-Nov-2021	ALK
Trial ID: SU-G-01	Version:	4.0	
EudraCT No. 2020-000455-12	Status:	Final	
CONFIDENTIAL	Page:	47 of 77	

11.16 Electronic diary and patient reported outcome questionnaires

During the trial, the subject will complete an eDiary. The eDiary is a hand-held electronic device that will be issued to the subjects at visit 3. Subjects will be instructed by the investigator in how to fill in the eDiary.

The following items will be provided in the eDiary at pre-specified intervals during EGPS (see the flow chart and Appendix 5):

- Rhinoconjunctivitis quality of life questionnaire (RQLQ)
- Rhinoconjunctivitis symptoms
- Use of rhinoconjunctivitis rescue medication for treatment of rhinoconjunctivitis

11.16.1 Symptom assessment: Rhinitis and conjunctivitis symptoms

Subjects should be instructed by the investigator or delegated staff on how to complete symptom assessments and record the results in the diary on a daily basis – in the evening.

A total of 6 allergic symptoms, 4 rhinitis and 2 conjunctivitis symptoms should be measured on a scale from no symptoms to severe symptoms.

The subject should be instructed in the symptom score using the following definitions:

- 0 No symptoms no sign/symptom evident
- 1 Mild symptoms symptom clearly present, but minimal awareness; easily tolerated
- 2 Moderate symptoms definite awareness of symptom that is bothersome but tolerable

3 - Severe symptoms - symptom that is hard to tolerate; causes interference with activities of daily living and/or sleeping

The 6 symptoms are classified in 2 groups as follows:

Nose symptoms:

- Runny nose
- Blocked nose
- Sneezing
- Itchy nose

Eye symptoms:

- Gritty feeling/red/itchy eyes
- Watery eyes

11.16.2 Medication assessment

Subjects are provided with open-label rhinoconjunctivitis rescue medication to be used as needed for treatment of their rhinoconjunctivitis symptoms not controlled by the IMP. Subjects should be instructed to report their use of rhinoconjunctivitis rescue medication via the daily diary. As suggested in an European Academy of Allergy and Clinical Immunology (EAACI) position paper on standardisation of clinical outcomes (Pfaar et al. 2014) the subjects should be instructed to start with antihistamine tablets and/or eye-drops. Treatment with nasal steroids should only be initiated if antihistamines and/or eye drops do not alleviate the symptoms.

Clinical trial protocol Trial ID: SU-G-01 EudraCT No. 2020-000455-12 CONFIDENTIAL
 Date:
 12-Nov-2021

 Version:
 4.0

 Status:
 Final

 Page:
 48 of 77

The medication use will be scored as shown in Table 10.

11.16.4 Rhinoconjunctivitis quality of life questionnaire

The quality of life will be assessed by the standardised RQLQ(S) questionnaire (Juniper et al. 1999) included in the electronic diary. RQLQ questionnaire contains 28 questions that are scored in 7-point scale (0 = not impaired at all; 6 = severely impaired). Questions are divided in 7 domains (activity limitations). The overall RQLQ score is derived by taking the average of 7 domain scores.

11.17 Paper questionnaire

Health-related quality of life assessment

The health-related quality of life will be assessed using the

12 SAFETY PROCEDURES

Information about AEs, whether reported by the subject, discovered by the investigator by reviewing eDiary records, detected through physical examination, laboratory test or other means, must be collected and recorded on the AE form and followed up as appropriate. Evaluation of AEs including severity, causality, outcome and seriousness assessments must be performed by a physician.

Any AE occurring from the time the informed consent was signed by the subject and until the last follow-up phone contact must be recorded and reported on the AE page in the eCRF. This includes all AEs, even AEs occurring before the subject is administered the IMP and whether or not AEs are observed in connection with the trial assessments and conduct of the trial.

Clinical trial protocol	Date:	12-Nov-2021			
Trial ID: SU-G-01	Version:	4.0		1	
EudraCT No. 2020-000455-12	Status:	Final			
CONFIDENTIAL	Page:	49 of 77	_		

12.1 Definitions

Adverse events

An AE is any untoward medical occurrence in a clinical trial subject, and which does not necessarily have a causal relationship with the administered IMP.

An AE can therefore be any unfavourable and unintended sign (including e.g. an abnormal laboratory finding or medication error), symptom or disease, whether or not considered related to the IMP.

The following events should not be recorded as AEs:

- A pre-planned procedure, e.g. a surgical intervention, unless the condition for which the procedure was planned has worsened since the informed consent form was signed.
- Pre-existing conditions documented as medical history. However, any worsening in severity or frequency of a pre-existing condition during the clinical trial period must be regarded as an AE.

Serious adverse events

An SAE is any untoward medical occurrence or effect that at any dose:

- Results in death
- Is life-threatening (this refers to an event in which the subject was at risk of death at the time of the event; it does not refer to an event that hypothetically might have caused death if it had been more severe)
- Requires in-subject hospitalisation, regardless of duration, or prolongation of existing hospitalisation
- Results in persistent or significant disability or incapacity
- Is a congenital anomaly or birth defect
- Is judged to be medically important (this refers to an event that may not be immediately lifethreatening or result in death or hospitalisation, but may jeopardise the subject or may require intervention to prevent one of the other outcomes listed above)

Events of medication error, overdose and abuse

Medication error, misuse, overdose and abuse of IMP(s) must always be collected in line with adverse event reporting, with or without associated AEs.

- Medication error: Any unintended failure in the medication treatment process that leads to, or has the potential to lead to, harm to the subject.
- Overdose: Any cumulative dose taken in one day that exceeds the dose intended by this protocol, regardless of whether the dose has caused any AEs
- Abuse: Persistent or sporadic, intentional excessive use which is accompanied by harmful physical or psychological effects
- Misuse: Intentional and inappropriate use

Events of special interest (ESI)

Selected (non-serious or serious) AEs will be considered ESIs. ESIs are events that are considered critical for the evaluation of the product's safety profile and for which additional data will be collected. ESIs for this trial are:

- Systemic allergic reactions including anaphylaxis
- Events treated with adrenaline/epinephrine
- Severe local swelling of the mouth and/or throat
- Eosinophilic oesophagitis

Clinical trial protocol	Date:	12-Nov-2021		
Trial ID: SU-G-01	Version:	4.0		
EudraCT No. 2020-000455-12	Status:	Final		
CONFIDENTIAL	Page:	50 of 77	 	

Significant laboratory event

A significant laboratory event should be recorded as an AE if one of the following is applicable:

- It is clinically significant (medical judgement by investigator)
- It leads to a change or discontinuation of treatment
- It fulfils a seriousness criterion
- It indicates a potential safety risk to the subject
- If Hy's law is fulfilled; AST and/or ALT ≥3 times upper normal limit and bilirubin ≥2 times upper normal limit and ALP is not >2 times upper normal limit

12.2 AE assessments

12.2.1 Severity

The severity of an AE is a clinical observation assessed by the investigator using the following definitions:

- Mild: Transient symptoms, no interference with the subject's daily activities
- Moderate: Marked symptoms, moderate interference with the subject's daily activities
- Severe: Considerable interference with the subject's daily activities, unacceptable

12.2.2 Causal relationship to IMP

The causal relationship between an AE and the IMP is assessed by the investigator using the following definitions:

- Possible: A reasonable possibility of a causal relationship between the event and the IMP.
- Unlikely: The event is most likely caused by a different aetiology than the IMP.

For SAEs assessed as unlikely and possible related to IMP, the most likely alternative aetiology should be provided.

12.2.3 Outcome

The outcome of an AE is assessed by the investigator using the following definitions:

- Recovered: Fully recovered or the condition has returned to baseline
- Recovered with sequelae: As a result of the AE the subject suffered persistent disability/incapacity. If the sequela qualifies as a SAE, the AE must be reported as such
- Not recovered: The condition has not returned to baseline however, symptoms may have improved
- Fatal: Event that results in death
- Unknown: The outcome is unknown. This term should only be used when no other definition is possible e.g. the subject is lost to follow-up

12.3 Collection, recording and reporting of AEs

AEs must be recorded on the AE form in the eCRF with the initial eCRF report containing as much information as possible. One single AE form must be used per AE from start to resolution. For SAEs and ESIs, additional information will be collected. For each of the 4 pre-defined ESIs, the

Clinical trial protocol	Date:	12-Nov-2021	
Trial ID: SU-G-01	Version:	4.0	
EudraCT No. 2020-000455-12	Status:	Final	
CONFIDENTIAL	Page:	51 of 77	

investigator must fill out a specific eCRF ESI form with additional questions, in order to ensure that all relevant data is captured.

If the same type of AE occurs more than 1 day in a row with the same pattern (e.g. itching in the mouth for 5-10 minutes after intake of IMP) it is considered a recurrent AE. The AE form should be filled in with the start date and the description. If the AE no longer reoccurs after IMP intake, the AE form should be completed with a stop date. If the AE then re-appears on a subsequent day, a new AE form should be filled in.

The investigator should record the diagnosis, if available. If no diagnosis is available, the investigator should record each sign and symptom as individual AEs. Further, the diagnosis of the underlying disease should be reported instead of a procedure performed due to the disease (e.g. if a subject undergoes surgery due to appendicitis, appendicitis, and not the surgery performed, should be reported as the AE).

12.3.1 Reporting of SAEs

The investigator must report all SAE (initial as well as follow-up) to ALK within 24 hours after obtaining knowledge of the information. SAEs will automatically be sent to ALK via the eCRF system. In case the eCRF system is unavailable during the 24-hour reporting timeline, SAEs (including relevant data e.g. demography, medical history, concomitant medication) must be reported by email or fax to ALK. For all ESIs, additional information specific to the ESI in question will be collected in the eCRF.

Any specific eCRF ESI form and non-serious AEs should be reported within 5 working days after obtaining knowledge of the information.

If requested, please forward supporting documents to ALK via fax. Please state the trial ID and the subject and site ID on all documents.

IMPORTANT: Any information that could reveal the identity of the trial subject must be hidden or removed in the source documentation. Also, information that is not relevant for the subject and the subject's condition must be hidden or removed.

Email address:	<	>
Fax number:		
Emergency phone:		

The assessment of listedness is performed by ALK according to the reference safety information in the current version of the IB.

ALK will inform the regulatory authorities and IECs/IRBs in accordance with local requirements in force and the ICH guidelines for GCP (ICH 1996).

12.3.2 Follow-up on AEs and SAEs

SAEs must be followed up until resolution and until all queries have been resolved. The investigator must respond to SAE follow-up requests from ALK without delay and no later than 7 days after receiving the request.

For chronic diseases ongoing SAEs can be closed at the end of trial (visit 9) with the term "not recovered" (as evaluated upon medical evaluation by the investigator or the sponsor).

Clinical trial protocol	Date:	12-Nov-2021	
Trial ID: SU-G-01	Version:	4.0	
EudraCT No. 2020-000455-12	Status:	Final	
CONFIDENTIAL	Page:	52 of 77	

The investigator must ensure that the worst-case severity and seriousness of an event is kept throughout the trial.

Non-serious AEs must be followed up until resolution or until the end of trial (visit 9).

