Source documents	Source documents are original documents, data, and records from which the subjects' electronic case report form (eCRF) data are obtained. These include, but are not limited to, hospital records (from which medical history and concomitant medication may be summarised into the eCRF), clinical and office charts, laboratory and pharmacy records, diaries, microfiches, radiographs, and correspondence
Systemic corticosteroids	Oral, intramuscular, or intravenously administered corticosteroids
TEAE	TEAEs are defined as adverse events with start date and/or time on or after the time of first IMP administration and no later than 7 days after last IMP administration
Trial completion	The trial is completed once the integrated clinical trial report (ICTR) is signed
Trial discontinuation date	Date of subject trial discontinuation. In case of subjects lost to follow-up, the discontinuation date is defined as the date the investigator/sponsor decides to discontinue the subject

Protocol versions

Date	Version	Description of document	Rationale for amendment
29-Jan-2020	1.0	Final Protocol	N/A
11-Mar-2020	2.0	Final Protocol	Version update to align with IB
23-Oct-2020	3.0	Final Protocol	 Key changes: To address EMA recommendations in the 'Guidance on the Management of Clinical Trials during the COVID-19 (Coronavirus) pandemic' (EMA 2020) FEV₁ removed from screening visit 1 and from subsequent visits after randomisation visit 2 Oropharyngeal exam removed from screening visit 1 and from subsequent visits after randomisation visit 2 Addition of retention TC between visits V5 and V6 Removal of visit schedules/content from section 10. This section is not mandatory, is repetitive to the flow chart and assessments and creates a risk for error Estimand has been added as per ICH E9 (R1) addendum on estimands and sensitivity analysis in clinical trials to the guideline on statistical principles for clinical trials (Step 5) (ICH 2020)

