12-Nov-2021	4.0	Final Protocol	 Key changes List of appendices updates Flowchart: Time window for V4 and V7 expanded to allow up to 14 days prior to EGPS. Footnote 1 updated with 'optional' referring to TC1 and updated year of randomisation to 2021. 3.4: End of trial definition updated to the date of the last follow-up phone visit (TC follow-up) for the last subject in the trial. 7.: Table 2 updated due to reassessment of criticality of restricted and prohibited concomitant medication. 11.4: clarification on stratification added to medical history: A subject should be stratified as asthmatic if they have been diagnosed and/or treated for asthma in adulthood. 11.14: Assessments reordered to ease readability 12.1: Deletion of bullet stating that events defined as efficacy endpoints should not be recorded as AEs. 12.1: Addition of bracket in sentence: Selected AEs (nonserious or serious) will be considered ESIs 12.3 and 12.3.1 Specification of ESI forms and procedures 15.11.4 Correction of undefined reference Appendix 3 updated due to change of central lab and CRO legal entity and contact details

EudraCT No. 2020-000455-12Status:FinalCONFIDENTIALPage:16 of 77

Flow chart

Visit ID:	Protocol section	V1	V2	TC1	∨3	V4	V5	TC2	V6	V7	V8	V9	TC Follow- up	Unsched- uled visit
Visit: V=Site Visit TC=Telephone Contact		Screening	Random- isation	Optional between V2 and V3 ¹	1 st off- season	1 st pre- EGPS ²	1 st on- season	Retention between V5 and V6	2 nd off- season	2 nd pre- EGPS ²	2 nd on- season	End of trial	Post- treat- ment	
Time Window		At least 3 days before V2	At least 16 weeks before start of 1 st EGPS ²	November 2021	January 2022	14 to 0 days before start of 1st EGPS ²	7 to 0 days before expected PGPS ³	4-12 weeks before V6	January 2023	14 to 0 days before start of 2 nd EGPS ²	7 to 0 days before expected PGPS ³	1 to 7 days from end of 2 nd EGPS ²	4 to 10 days after V9	As necessary
Informed consent	11.1	х												
Demography and body measurements	11.3	х												
Smoking habits	11.5	х												
Medical history	11.4	х												
In-/exclusion criteria	4.1/4.2	х	х											
Randomisation	6		х											
Urine pregnancy test ⁴	11.10	(X)	(X)		(X)	(X)	(X)		(X)	(X)	(X)	(X)		(X)
Physical examination	11.8	Х										х		(X)

¹ An optional retention telephone contact for those subjects randomised between start of August and end of November 2021

² EGPS- entire grass pollen season (see Appendix 5)

³ PGPS- peak grass pollen season (see Appendix 5)

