⁴ For females of child-bearing potential, urine pregnancy tests should be performed at each visit and if a menstrual period is missed.

Clinical trial protocol Trial ID: SU-G-01 EudraCT No. 2020-000455-12 CONFIDENTIAL

Visit ID:	Protocol section	V1	V2	TC1	V3	V4	V5	TC2	V6	V7	V8	V9	TC Follow- up	Unsched- uled visit
Visit: V=Site Visit TC=Telephone Contact		Screening	Random- isation	Optional between V2 and V3 ¹	1 st off- season	1 st pre- EGPS ²	1 st on- season	Retention between V5 and V6	2 nd off- season	2 nd pre- EGPS ²	2 nd on- season	End of trial	Post- treat- ment	
Oropharyngeal examination	11.8		х											(X)
Vital signs	11.12	Х	х		х	х	Х		х	х	х	Х		(X)
Lung function test	11.7		х											(X)
Blood and urine samples for safety laboratory assessments	11.13	х										x		(X)
Blood sample for specific IgE	11.14	Х												
	11.14	х			x	х			x			x		(X)
Blood sample for biobanking⁵	11.15	(X)										(X)		
SPT	11.11	Х	(X)											(X)
Intake of IMP at clinic	9.1/9.2		х											
Instruct the subject in use of IMP	9.1/9.2		х											
Record previous and concomitant medication	11.6	х	х	х	x	х	х	х	х	x	х	х	х	x
Assess and/or record AEs	12.2	х	х	Х	х	х	Х	Х	х	х	Х	х	Х	х
Assess eosinophilic eosophagitis	11.9	Х	Х		Х	х	Х		х	х	Х	х		(X)
Dispense IMP	8.1		х		Х	х	Х		х	Х	Х			(X)

⁵ Only if biobanking specific informed consent has been signed and according to country specific regulations.

Clinical trial protocol Trial ID: SU-G-01 EudraCT No. 2020-000455-12 CONFIDENTIAL

Visit ID:	Protocol section	V1	V2	TC1	V3	V4	V5	TC2	V6	V7	V8	∨9	TC Follow- up	Unsched- uled visit
Visit: V=Site Visit TC=Telephone Contact		Screening	Random- isation	Optional between V2 and V3 ¹	1 st off- season	1 st pre- EGPS ²	1 st on- season	Retention between V5 and V6	2 nd off- season	2 nd pre- EGPS ²	2 nd on- season	End of trial	Post- treat- ment	
Dispense rescue medication	8.2					х	(X)			(X)	(X)			(X)
Trial medication collection, compliance check compliance and drug accountability	8.5				x	x	x		x	x	x	x		x
	11.17		х									х		
Issue and instruct in use of E- diary/LogPad	11.16				x									
Instruct in use of E- diary/LogPad	11.16					x	(X)			x	(X)			
eDiary completion:	11.16.5						X ₆							
eDiary completion: • RQLQ	11.16.4				х	X	X ⁷			X	X ⁷			
eDiary completion: • Symptoms • Medication	11.16.1/ 11.16.2					x	X ⁷			x	X ⁷			
eDiary completion:	11.16.3					x	X ⁷			x	X ⁷			
Review eDiary recordings	11.16						Х		х	Х	Х	Х		(X)
Collect eDiary												x		

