3.4 End of trial definition

A subject is considered to have completed the trial if he/she has completed the last scheduled visit (V9).

The end of the trial is defined as the date of the last follow-up phone visit (TC follow-up) for the last subject in the trial.

Clinical trial protocol	Date:	12-Nov-2021	
Trial ID: SU-G-01	Version:	4.0	
EudraCT No. 2020-000455-12	Status:	Final	
CONFIDENTIAL	Page:	28 of 77	

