TOS	Total analysis set
WHO	World Health Organization

2 Table of definitions

AE	An AE is any untoward medical occurrence in a clinical trial subject, and which does not necessarily have a causal relationship with the administered IMP.
Completed treatment	A subject is considered to have completed treatment if he/she has been randomized and has not discontinued treatment.
Completed subject	A randomised subject is considered completed if he/she has not discontinued the trial before V9.
Completion date	For each completed subject, the date of the last scheduled procedure/end of trial visit(V9).
Concomitant medication	All medications being continued by a subject on entry into the trial and all medications given in addition to the background treatment during the trial.
Date of last contact	Date of the last contact, either by telephone or in a visit.
End of trial	The end of the trial is defined as the date of V9.
Estimand	A precise description of the treatment effect reflecting the clinical question of interest posed by the trial objective. It summarises at a population-level what the outcomes would be in the same patients under different treatment conditions being compared (ICH 2020).
Grass pollen season	Start date: The first day of 3 consecutive days with (non-missing) pollen count larger than or equal to 10 grains/m ³ .
	 Stop date: The last day before 3 consecutive days with (non-missing) pollen count less than 10 grains/m³.
Peak grass pollen season	The 15 days period with the highest average pollen count during the entire grass pollen season.
IMP	A pharmaceutical form of an active substance or placebo being tested or used as a reference in a clinical trial, including products with a marketing authorisation used or assembled (formulated or packaged) in a way different from the authorised form, or when used for an unauthorised indication, or when used to gain further information about the authorised form.
Intercurrent events	Events occurring after treatment initiation that affect either the interpretation or existence of the measurements associated with the clinical question of interest. It is necessary to address intercurrent events when describing the clinical question of interest in order to precisely define the treatment effect that is to be estimated (ICH 2020).
LSLV	Last scheduled physical visit for any subject (V9).

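### Required follow-up of non-serious AEs ends at visit 9, before AE collection ends at the follow-up call; separately, the call window does not guarantee cover of the 7-day TEAE period

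*Protocol*

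**What the plan says.** Protocol 12.3.2 sets the follow-up limits. For non-serious events: "Non-serious AEs must be followed up until resolution or until the end of trial (visit 9". For serious events: "SAEs must be followed up until resolution and until all queries have been resolved"; ongoing SAEs in chronic diseases may be closed at V9 after medical evaluation.

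Collection runs longer. Under protocol section 12, AEs from consent "until the last follow-up phone contact must be recorded and reported on the AE page in the eCRF". The flow chart places that call "4 to 10 days after V9" and marks AE assessment at it.

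The flow chart row "Blood and urine samples for safety laboratory assessments" is marked at V1 and V9, with an optional mark for unscheduled visits. The physical examination row has the same pattern. The sampling tables in 11.13 confirm two safety samples for each of haematology, chemistry and urinalysis.

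The end of trial is defined in more than one way. Protocol 3.4: "The end of the trial is defined as the date of the last follow-up phone visit (TC follow-up". SAP section 2: "The end of the trial is defined as the date of V9".

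Both documents count an AE as treatment-emergent if it starts on or after the first dose and "no later than 7 days after last IMP administration".

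**The concern.** A rule that ends follow-up before collection ends leaves some events that must be entered in the eCRF but that nobody is explicitly required to pursue. The gap lies where the scheduled safety data lie, because V9 is the only planned post-baseline look at laboratory values and physical examination.

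Samples go to a central laboratory, which reports after analysis (protocol 11.14 and 14.4). A V9 result will therefore probably reach the site after the 12.3.2 limit has passed. Protocol 12.3.4 requires significant results to be recorded as AEs, and it lists fulfilment of Hy's law separately from meeting a seriousness criterion. Events of special interest may also be non-serious (protocol 12.1). SAP 6.4.2.2 tabulates AE outcome, so an outcome not pursued after V9 may be reported less completely than the planned call would allow.

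The second matter is separate. If the call comes less than 7 days after the last dose, part of the period in which an AE counts as treatment-emergent is not observed. After the call, protocol 12.3.6 asks only for IMP-related SAEs and for pregnancies during exposure.

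**Working it through.** The plan gives no figure on either matter, so there is nothing to reproduce. The first is a comparison of rules; the second is a count of days.

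**Follow-up limit against collection period**

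| Event | Must be recorded? | Follow-up required by 12.3.2 |
|---|---|---|
| Non-serious finding at the V9 examination that meets the AE definition | Yes (11.8, section 12) | 0 days: found on the day the limit falls |
| Significant, non-serious result from the V9 sample | Yes (12.3.4) | None: the limit has passed if the report arrives after V9 (inferred from central analysis) |
| Non-serious AE starting between V9 and the call | Yes (section 12) | None: the limit passed before onset |
| SAE | Yes | To resolution; chronic-disease SAEs may be closed at V9 |

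If the limit were the call, required follow-up in the first row would rise from 0 days to 4–10 days.

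**TEAE period against call window**

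Inputs:
- *t*, days from V9 to the call: 4 to 10, so 7 permitted values (flow chart).
- *g*, days from last dose to V9: not fixed exactly. The synopsis has treatment continue to the end of the 2023 EGPS, and the flow chart puts V9 1 to 7 days after that, so *g* = 1 to 7. Protocol 8.3 has IMP packed to last until the End of Trial visit, which leaves *g* = 0 possible.
- TEAE period: 7 days after the last dose (definitions tables of both documents).

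Formula: shortfall = max(0, 7 − (*g* + *t*)).

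- *g* = 0: *t* = 4, 5, 6 give 3, 2, 1 days. That is 3 of 7 call days (3/7 = 43%).
- *g* = 1: *t* = 4, 5 give 2, 1 days. That is 2 of 7 (29%).
- *g* = 1 to 7: 7 × 7 = 49 combinations. Only (*g*, *t*) = (1, 4), (1, 5) and (2, 4) fall short, by 2, 1 and 1 days. That is 3 of 49 (6%).
- *g* ≥ 3: *g* + *t* is at least 7, so the shortfall is 0.

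These are shares of permitted day combinations. They equal shares of subjects only if calls and visits are spread evenly over their windows, which the documents do not say.

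Moving the 12.3.2 limit to the call would leave every shortfall unchanged. TEAE status depends on onset date, and onsets are already collected to the call; the cause is the 4-day lower bound of the call window.

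**Timing**

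SAP 3.2.2 gives the last subject's last visit (V9) as 22-Sep-2023. Ten days later is 2-Oct-2023, before the SAP date of 27-Oct-2023. Calls made within the window were therefore complete when the SAP was finalised.

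**The case against.** The strongest reply is that the gap is one of wording. Section 12 requires AEs, including those found by examination or laboratory test, to be followed up as appropriate. Investigators must review laboratory values immediately (11.14). One AE form runs from start to resolution (12.3). AEs are assessed at the call, and repeat laboratory tests and examinations are possible at unscheduled visits. SAEs are followed to resolution. All of this stands, and it means a reader should not infer that V9 abnormalities get no follow-up. What is missing is a required period for non-serious events. A general duty does not clearly override an explicit stopping point, and sites may read the two differently.

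It can also be said that the end-of-trial wording in 12.3.2 is only the visit's name: the flow chart titles V9 that way, and the protocol's definitions table separates the subject's end-of-trial visit from the overall end of the trial. That reading is fair and weakens the conflict with 3.4. It does not move the follow-up limit, which is still V9.

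Three further inferences go too far:
- Closure as not recovered is permitted at V9 only for SAEs in chronic diseases. Nothing extends it to IMP-related reactions generally.
- The TEAE shortfall does not come from 12.3.2.
- The 43% figure needs a last dose on the day of V9. Packing enough drug to reach V9 is not an instruction to dose that day, and the synopsis supports an earlier stop, which gives 6%.

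The documents give no rate of significant findings at V9, so the number of subjects affected cannot be stated. The same cut-off applies to both blinded arms.

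**Conclusion.** The point holds in limited form. As written, 12.3.2 leaves non-serious findings at V9, and non-serious AEs starting between V9 and the call, with no required follow-up, although AE recording continues for 4 to 10 more days and V9 is the only scheduled post-baseline occasion for safety laboratory tests and physical examination. This rests on the text of the rules; only the late arrival of V9 laboratory results is inferred. The SAP's end-of-trial definition also differs from protocol 3.4.

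Separately, the call window does not guarantee cover of the TEAE period. The loss is at most 3 days if the last dose is on V9 and at most 2 days if it is at the end of the EGPS. It is nil once the call is at least 7 days after the last dose.

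Both matters bear on the completeness of safety data. Neither touches the efficacy analyses.

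**What to change.** 1. Reconcile protocol 12.3.2 with section 12, 3.4 and the definitions table so that the limit for non-serious AE follow-up, and the closing point for chronic-disease SAEs, is not earlier than the end of AE collection, which is the call already planned. State how significant V9 findings are handled, since a telephone contact does not itself provide a repeat test.
2. Align the end-of-trial definition in SAP section 2 with protocol 3.4.
3. Reconcile the flow chart's call window with the TEAE definition so that the call is not earlier than the end of the 7-day post-dose period.
4. For this trial, where the last visit has taken place, check before database lock the outcomes recorded for V9 findings and each subject's interval from last dose to call. Report how many subjects have an incompletely observed TEAE period, by arm.

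The cost is a wording change, a narrower window for an existing call and a few extra contacts. The check in step 4 uses dates the trial should already hold; incomplete last-dose dates are imputed under SAP 9.4.2 and should be flagged in that count.
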